12.7.3. Physical Examination Findings

All physical examination results will be presented in a data listing.

12.7.4. Vital Signs/Height and Weight

Vital sign measurements (diastolic blood pressure, systolic blood pressure, respiratory rate, pulse rate, body temperature, weight and height) will be presented in a data listing.

12.8. Interim Analysis

Not applicable.

12.9. Statistical Power and Sample Size Consideration

Formal sample size calculations were not performed.

12.10. Deviations From Statistical Analysis Plan

Any deviations from the planned statistical analysis will be described and justified in the final clinical study report as appropriate.

13. ADVERSE EVENTS AND SERIOUS ADVERSE EVENTS

13.1. Safety

For safety information about Acthar refer to the most recent version of the Prescribing Information ([Mallinckrodt ARD LLC, 2015](#)).

13.2. Definitions

Adverse Event

An AE is any untoward or undesirable medical occurrence in a subject who is administered an IMP, which does not necessarily have to have a causal relationship with this treatment. Examples of AEs include but are not limited to:

- Clinically significant laboratory findings.
- Clinically significant changes in physical examination findings.
- An AE occurring due to IMP overdose whether accidental or intentional.
- An AE occurring from IMP abuse.
- An AE associated with IMP withdrawal.
- Unexpected AE.

An unexpected AE is defined as an AE, the nature and severity of which is not consistent with the applicable product information in the most recent version of the Investigator's Brochure.

Serious Adverse Event

A serious adverse event (SAE) is defined as any untoward medical occurrence that at any dose results in any of the following outcomes:

- Death.
- A life-threatening AE.
- Inpatient hospitalization or prolongation of existing hospitalization.
- A persistent or significant incapacity or substantial disruption of the ability to conduct normal life functions.
- Results in a congenital anomaly/birth defect.

Important medical events that may not result in death, be life-threatening, or require hospitalization may be considered serious when, based upon appropriate medical judgment, may jeopardize the subject or subject and may require medical or surgical intervention to prevent one of the outcomes listed above. Examples of such medical events include allergic bronchospasm requiring intensive treatment in an emergency department or at home, blood dyscrasias or convulsions that do not result in inpatient hospitalization, or the development of drug dependency or drug abuse.

Death

Death is an outcome of an event. The event that resulted in death should be recorded and reported on the SAE Form. All causes of death must be reported as SAEs. The investigator should make every effort to obtain and send death certificates and autopsy reports to Mallinckrodt.

Life-threatening Event

A life-threatening event refers to immediate risk of death as the event occurred per the reporter. A life-threatening event does not include an event that, had it occurred in a more severe form, might have caused death but, as it actually occurred, did not create an immediate risk of death. For example, hepatitis that resolved without evidence of hepatic failure would not be considered life-threatening, even though hepatitis of a more severe nature can be fatal. Similarly, an allergic reaction resulting in angioedema of the face would not be life-threatening, even though angioedema of the larynx, allergic bronchospasm, or anaphylaxis can be fatal.

Hospitalization

Hospitalization is defined as an official admission to a hospital. Hospitalization or prolongation of a hospitalization constitutes a criterion for an AE to be serious; however, it is not in itself considered an SAE. In absence of an AE, a hospitalization or prolongation of a hospitalization should not be reported by the investigator as an SAE. Such situations include, but are not limited to, the following:

- A hospitalization or prolongation of hospitalization is needed for a procedure required by the protocol.
- A hospitalization or prolongation of hospitalization is part of a routine procedure followed by the center (eg, stent removal after surgery). This should be recorded in the study file.
- A hospitalization for a preexisting condition that has not worsened.

Note that a visit to the emergency department or other hospital department of less than 24 hours that does not result in admission (unless considered "important medical event" or life-threatening event) is not considered an SAE in Mallinckrodt clinical studies.

13.3. Adverse Event and Serious Adverse Event Classifications

IMP Relatedness

The following classifications should be used when evaluating the relationship of AEs or SAEs to study treatment ([Table 7](#)).

Table 7: Adverse Event Relationships

Relationship	Definition
Not Related	No relationship between the experience and the administration of study treatment; related to other etiologies such as concomitant medications or subject's clinical state.
Unlikely Related	The current state of knowledge indicates that a relationship is unlikely.
Possibly Related	A reaction that follows a plausible temporal sequence from administration of the study treatment and follows a known response pattern to the suspected study treatment. The

Relationship	Definition
	reaction might have been produced by the subject's clinical state or other modes of therapy administered to the subject.
Related	A reaction that follows a plausible temporal sequence from administration of the study treatment and follows a known response pattern to the suspected study treatment and can be confirmed with a positive re-challenge test or supporting laboratory data.

Severity Assessment

For purposes of consistency, if required the investigator may use the intensity grades presented in [Table 8](#).

Table 8: Adverse Event Severity Grades

Grade	Definition
Mild	Does not interfere with subject's usual function and activities
Moderate	Interferes to some extent with subject's usual function and activities
Severe	Interferes significantly with subject's usual function and activities

If an AE increases in severity (eg, from moderate to severe); decreases in severity (eg, changes from moderate to mild); or there is a change in seriousness, a new AE will be opened and the original AE will be closed. If an AE is still ongoing at the time of a subject's completion of the follow-up visit, the resolution/stop date and time is left blank.

To ensure there is no confusion or misunderstanding of the difference between the terms "serious" and "severe," which are not synonymous, the following note of clarification is provided:

The term "severe" is used to describe the intensity (severity) of a specific event (as in mild, moderate, or severe myocardial infarction); the event itself, however, may be of relatively minor medical importance (such as a severe headache). This is not the same as "serious," which is based on the subject/event outcome or action criteria usually associated with events that pose a threat to a subject's life or functioning. Seriousness (not severity) serves as a guide for defining regulatory reporting obligations.

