12.7.1. Adverse Events

AEs will be coded using MedDRA. All AEs will be presented in a data listing. Only treatment-emergent adverse events (TEAEs) will be included in all summaries.

TEAEs, treatment related TEAEs, severity of TEAEs, and TEAEs leading to early discontinuation will be summarized by system organ class and preferred term for all dosed subjects at the treatment level and overall. All TEAEs leading to early discontinuation will be presented in data listings.

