13.4. Adverse Event and Serious Adverse Event Recording and Reporting

AEs and SAEs will be collected from signing of the ICF through completion of the end of study/early termination visit. All AEs and SAEs should be recorded in source documents; all AEs and SAEs that occur following the first dose of IMP should also be recorded in the eCRF. The investigator is required to record the AE or SAE regardless of the severity of the event or its relationship to study treatment. Prior to the first dose at the Baseline Visit/Visit 2, only AEs and SAEs related to study procedures will be recorded on the eCRF. The investigator must follow up on all AEs and SAEs reported to have occurred 30 days after study completion until the event has resolved or stabilized or at such time the investigator refers the subject to a nonstudy

physician. The investigator will document the further follow-up information in the subject's source document.

During the period specified above, the investigator will:

- Record all AEs and SAEs from the signing of the ICF through the completion of the End of Study/Early Termination visit
- Report all SAEs on an SAE Report Form to Global Pharmacovigilance.
- Report all pregnancies to Global Pharmacovigilance on the Pregnancy Surveillance Form.
- Submit any Expedited Safety Report or Suspected Unexpected Serious Adverse Reaction from Global Pharmacovigilance to the IRB/IEC.

The reporting requirements for AEs are summarized in [Table 9](#).

Table 9: Reporting Requirements for Adverse Events

Seriousness	Reporting Time	Type of Report
All Serious	Within 24 hours of first knowledge of event	Initial report on the SAE Form, appropriate eCRF, and source document
	Within 24 hours of receipt of follow-up information	Follow up report on the SAE Form, appropriate eCRF, and source document
Nonserious	Per case report form submission procedure	Appropriate eCRF and source document

Adverse Events

AEs can be reported spontaneously or elicited during open-ended questioning (ie, "How have you been feeling since your last visit?"), examination, or evaluation of a subject. Signs and symptoms must be recorded using standard medical terminology. For subjects incapable of giving consent, the legally acceptable representative may provide information regarding the subject's status.

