All fields on the AE CRF page should be completed for each event with a full description of the event and date of onset/start and resolution/stop. A medical diagnosis if known, should be recorded in lieu of each individual sign and symptom associated with the diagnosis and experienced by the subject. If no medical diagnosis is known, the term used by the subject to describe the event or signs noted by the site personnel should be recorded.

Serious Adverse Events

Initial Reporting

SAEs (based on FDA/ICH definition of an SAE) require immediate reporting to Global Pharmacovigilance.

- For all SAEs, the investigator, or designee, must complete the SAE Report Form with the minimum information required by FDA and ICH and fax it to Mallinckrodt at [contact] or email at [contact] within 24 hours of first knowledge of the event even if the experience does not appear to be related to the IMP.
- The investigator, or designee, will receive acknowledgement of receipt of the SAE report form from Mallinckrodt.
- Should the investigator or designee have any difficulty in sending the SAE report, they may contact Mallinckrodt based on the information in the Study Operations Manual.
- If there is any doubt about whether the information constitutes an SAE, the information is to be treated as an SAE.

The investigator(s) or designee is required to submit the any expedited safety report or suspected unexpected serious adverse reaction to the responsible IRB/IEC.

The sponsor will ensure that any expedited safety report or suspected unexpected serious adverse reaction are submitted to the FDA and other regulatory agencies as appropriate.

Follow Up Reporting

The investigator or designee must complete an SAE report form for all follow-up information received and fax it to Mallinckrodt at [contact] within 24 hours of receipt.

The investigator(s) or designee will receive acknowledgement of receipt for each SAE report form from Mallinckrodt.

- The investigator or designee is required to provide all related information/supporting documentation of an SAE until the SAE is resolved or stabilized or the subject has been referred to a nonstudy physician for follow-up treatment.
- The investigator(s) or designee is required to submit the safety alert to the responsible IRB/IEC.
- The sponsor will ensure that any expedited safety report or suspected unexpected serious adverse reaction are submitted to the FDA and other regulatory agencies as appropriate.

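### Table 7 requires a known response pattern for both Possibly Related and Related, so a well-timed reaction of a new kind fits no relatedness grade and may drop out of the treatment-related TEAE summary

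*Combined protocol and SAP*

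**What the plan says.** Section 13.3 introduces Table 7 with an instruction: "The following classifications should be used when evaluating the relationship of AEs or SAEs to study treatment". The table has four grades.

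- Possibly Related: plausible timing after study treatment "and follows a known response pattern to the suspected study treatment". A second sentence allows that the subject's condition or another therapy might have been responsible.
- Related: the same two conditions, "and can be confirmed with a positive re-challenge test or supporting laboratory data".
- Unlikely Related: present knowledge points against a relationship.
- Not Related: there is no relationship, and the event is put down to something else.

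There is no grade for an event whose cause cannot be excluded or assessed.

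The grade feeds one planned output. Section 12.7.1 states: "TEAEs, treatment related TEAEs, severity of TEAEs, and TEAEs leading to early discontinuation will be summarized by system organ class and preferred term". Neither that section nor Section 13.3 says which Table 7 grades count as treatment-related.

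Recording does not depend on the grade. Section 13.4 says: "The investigator is required to record the AE or SAE regardless of the severity of the event or its relationship to study treatment". It also requires SAE reports within 24 hours "even if the experience does not appear to be related to the IMP".

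**The concern.** A causality scale for a safety study needs a place for a reaction nobody has described before. Table 7 has none, because it treats prior recognition of the pattern as a condition for suspecting the drug at all.

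This matters more here than it would in a controlled trial. Since Amendment 3 the primary objective is safety and tolerability (Section 4.1), and every subject receives Acthar (Section 5.1). No comparison group can show an excess of a new event. Of the summaries named in Section 12.7.1, the treatment-related one is the only one that speaks to attribution. Sections 12.7.2 to 12.7.4 offer only listings for laboratory, physical examination and vital sign data. If the wording is followed, that summary can omit the reactions that would be new information.

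The table does not define what makes a pattern known. About 60 subjects at about 100 sites (Section 5.4) is 60/100 = 0.6 subjects per site on average, so many investigators would interpret the phrase, each for very few subjects.

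**Working it through.** The plan gives no figure on this point and none is needed; the check is logical. Take three facts about an event: plausible timing, known pattern, and confirmation by re-challenge or laboratory data. Hold timing at yes and apply the Table 7 definitions from Section 13.3.

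| Known pattern | Confirmed | Possibly Related | Related |
|---|---|---|---|
| yes | no | met | not met |
| yes | yes | met | met |
| no | no | not met | not met |
| no | yes | not met | not met |

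The last two rows are the gap. In the fourth row a positive re-challenge does not rescue the event, because Related adds confirmation to the known pattern and does not accept it as a substitute.

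Next, the lower grades for those two rows. Not Related requires another cause, and by construction none has been found. Unlikely Related requires present knowledge to point against a relationship; having no knowledge of a pattern is not the same thing. The investigator must therefore choose a grade whose definition does not describe the event.

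Then the outputs in Sections 12.7.1 and 13.4, for an event placed in one of the lower two grades:

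- AE recording and listing: kept.
- Summary of all TEAEs: kept.
- Summary of TEAEs by severity: kept.
- Summary of TEAEs leading to early discontinuation: kept if the event led to discontinuation.
- SAE report to the sponsor: made, if the event is serious.
- Summary of treatment-related TEAEs: left out if treatment-related means Possibly Related plus Related. It would stay in only if Unlikely Related also counted and the investigator had chosen that grade.

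So one of the four TEAE summaries in Section 12.7.1 is exposed, conditional on a mapping that the documents do not state.

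**The case against.** Five arguments can be made on the other side.

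**The phrase can be read broadly.** Table 7 does not tie a known pattern to earlier FSGS cases. Section 3.4 discusses cortisol-equivalent exposure and Section 3.5 lists a wide range of risks, so much of what occurs could be called known. This stands as a limit on how often the gap would open. It does not close the gap for a reaction outside that range.

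**Little depends on the grade.** Relatedness is not part of the primary endpoints in Section 4.1, and recording, listing, the other TEAE tables and SAE reporting do not use it. This stands in full and sets the size of the point.

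**The mapping may be elsewhere.** Section 12.1 refers to a statistical analysis plan and Section 17 to eCRF instructions; either could define treatment-related. The documents reviewed here contain no such definition, so this stands as a caution. It would not repair Table 7.

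**Timing alone is too loose.** With dosing two or three times a week over 50 weeks, almost any event is plausibly timed. Simply deleting the pattern condition would make nearly everything possibly related. This stands, and the replacement wording has to deal with it.

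**Reporting of unexpected serious reactions.** A reader might infer that unexpected serious reactions would go unreported. Section 13.2 says "An unexpected AE is defined as an AE, the nature and severity of which is not consistent with the applicable product information", and Section 13.4 tells the investigator: "Submit any Expedited Safety Report or Suspected Unexpected Serious Adverse Reaction from Global Pharmacovigilance to the IRB/IEC". The documents do not support that inference. SAEs reach the sponsor whatever their Table 7 grade. The reports that the investigator forwards come from the sponsor's pharmacovigilance group. The sponsor's own causality rule is not given, and expectedness is judged against product information, which is a different test from Table 7. No reporting failure is shown.

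**Conclusion.** The point holds as a defect of wording with a limited but real consequence. As written, Table 7 gives no fitting grade to a well-timed reaction of a new kind, confirmed or not. That follows from the text without any assumption beyond reading the definitions literally. Omission from the treatment-related TEAE summary rests on one further assumption: that treatment-related means the top two grades.

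The size is the relatedness grade itself plus that one summary. The events would still be visible in the listing and in the summary of all TEAEs.

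The number of events affected cannot be estimated. A reader might try to infer it from the 24-patient FSGS experience in Section 3.1, but a reaction unseen in those patients is not the same as one with no known pattern. Sections 3.2, 3.4 and 3.5 describe an approved product with labelled risks and use in other conditions.

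The correction is worth making because the primary objective is safety, there is no control arm, and the change is small.

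**What to change.** 1. In Table 7, say that a known response pattern supports a relationship but is not required. Define Possibly Related as plausible timing where a causal role of the study treatment cannot reasonably be excluded. Define Related as plausible timing confirmed by re-challenge or supporting laboratory data. Keep the lower two grades for events with a more probable other cause, so that timing alone does not decide the grade.
2. In Section 12.7.1, state that treatment-related means Possibly Related or Related.
3. For AEs graded before the change, record which definition applied and show this with the summary. The re-consent notes in Section 1.4 (footnote c) and Section 8.1 suggest that subjects were enrolled before Amendment 3, so graded records probably exist. Do not re-grade them: the study is unblinded (Section 9.2), and retrospective grading invites hindsight bias.

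The cost is wording in two sections and a flag on existing AE records. Somewhat more events will be called related, so the treatment-related summary loses some specificity. It will also contain grades made under two definitions, which the flag makes visible but does not remove.

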4. OBJECTIVES

4.1. Primary Objective

Primary Objective	Primary Endpoints
To confirm the safety and tolerability of Acthar in the induction of remission of proteinuria in subjects with primary FSGS who are resistant to, or intolerant of, at least 1 prior immunosuppressive therapy	
 ● Severity and frequency of adverse events (AEs) ● Changes in physical findings ● Changes in clinical laboratory findings ● Changes in vital signs

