9.3.1. Dose Reduction

The dosing of Acthar should be tapered from 3x/week to 2x/week for safety reasons if a subject meets any of the following criteria:

- Development of accelerated hypertension (defined as systolic blood pressure \geq 180 *and* diastolic blood pressure \geq 100 mm Hg) that cannot be managed with adjustment of concomitant medications such as antihypertensive medications.
- Development of an edema score of 4 at any visit that cannot be managed with adjustment of concomitant medications such as diuretics (see [Section 24.2](#)).
- Development of congestive heart failure that cannot be managed with adjustment of concomitant medications such as diuretics and antihypertensive medications.
- Development of diabetic signs/symptoms (ie, HbA1c > 8%, or fasting plasma glucose > 126 mg/dL, or classic symptoms of hyperglycemia with random plasma glucose > 200 mg/dL).
- Development of any other AE of at least moderate intensity that cannot be managed with adjustment of concomitant medications.

Any subject whose dose is tapered for any of the reasons described above will have a Taper Safety Visit scheduled 2 weeks after the start of the taper.

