10.5. Vital Signs

Vital signs will be obtained after the subject has been seated for 5 minutes (minimum) and will include systolic and diastolic blood pressures, pulse rate, respiratory rate, and body temperature. Additionally, at the Screening Visit/Visit 1 and the Baseline Visit/Visit 2, blood pressure will be measured at least 3 times, with 5 minutes between assessments after the subject has been seated for a minimum of 5 minutes prior to the initial blood pressure assessment.

The investigator may perform additional unscheduled vital sign measurements to evaluate or manage a suspected AE. These unscheduled vital sign measurements should be obtained after the subject has been seated for at least 5 minutes, if possible. Unscheduled vital signs will be recorded.

At a minimum, the date of vital signs at the Screening Visit/Visit 1 will be recorded. The date and time for all other vital signs will be recorded.

Screening/Baseline

A subject with systolic blood pressure > 150 mm Hg and diastolic blood pressure > 90 mm Hg (average of 3 assessments) at the Screening Visit/Visit 1 or Baseline Visit/Visit 2 does not qualify for the study.

On Study Assessments

If an on-study vital sign is not in the reference range, an AE will be recorded if the investigator determines the change is clinically significant or requires a change in the subject's clinical management.

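### The only AE severity scale (Table 8) is optional and purely functional, so the planned severity summary could understate symptom-free laboratory and blood-pressure harms

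*Combined protocol and SAP*

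**What the plan says.** Section 4.1 lists four primary endpoints. The first is the severity and frequency of AEs. "Changes in clinical laboratory findings" is another, alongside physical findings and vital signs.

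Section 13.3 introduces the severity scale with "For purposes of consistency, if required the investigator may use the intensity grades presented in" Table 8. Mild is defined as "Does not interfere with subject's usual function and activities"; Moderate and Severe are some and significant interference with the same thing. The table has no criterion for a laboratory value, a vital sign or a need for treatment. No other AE severity scale appears in the documents. The edema score in Attachment 2 grades a physical sign and is not linked to AE severity.

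Measurements become AEs by three routes. Section 13.2 gives "Clinically significant laboratory findings" as an example of an AE. Section 10.7 has new or changed laboratory abnormalities of clinical significance reported as AEs, as appropriate. Section 10.5 says of an out-of-range on-study vital sign that "an AE will be recorded if the investigator determines the change is clinically significant or requires a change in the subject's clinical management". None of the three requires a symptom.

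For the analysis, section 12.7.1 states that "severity of TEAEs, and TEAEs leading to early discontinuation will be summarized by system organ class and preferred term". Sections 12.7.2 and 12.7.4 place laboratory results and vital signs in data listings.

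Section 9.3.1 names four dose-reduction criteria (accelerated hypertension, edema score, congestive heart failure, diabetic signs or symptoms) and then adds "Development of any other AE of at least moderate intensity that cannot be managed with adjustment of concomitant medications". Section 9.3.2 has a matching last bullet for discontinuation.

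**The concern.** The scale measures one thing, loss of function, while the AE definition admits events that need not affect function at all. Section 3.5 lists hypertension and hyperglycemia among the known risks of the product, and both can be found by measurement before the subject notices anything.

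The study has no control arm, so the distribution of AE severity is itself the tolerability result. If measured harms gather in the lowest grade because of how the scale is worded, no comparator shows it.

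Two further uses depend on the grade. Section 13.3 opens a new AE record when severity changes, so a laboratory AE that worsens without symptoms opens none on that ground. The catch-all bullets of 9.3.1 and 9.3.2 also turn on whether an event is at least moderate.

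Because the scale is optional, grading may also be inconsistent. About 60 subjects at about 100 sites is 60/100 = 0.6 subject per site on average, so few sites will grade enough events to settle on a convention.

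**Working it through.** The plan gives no figure to reproduce: no AE rate, no expected severity distribution, and section 12.9 states that no sample size calculation was done. The check is a side-by-side reading.

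**Step 1: can a symptom-free measurement be an AE?** Yes. Sections 10.5, 10.7 and 13.2 rest on clinical significance or, for vital signs, a change in management.

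**Step 2: what grade does Table 8 give it?** Three illustrative records, each assumed to cause no interference with usual function and to be judged clinically significant:

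| Record | AE through | Table 8, if applied | Position under 9.3.1 |
|---|---|---|---|
| HbA1c 9.0% | 10.7, 13.2 | Mild | Meets the diabetic criterion (HbA1c above 8%), whatever the grade |
| Blood pressure 185/105 mm Hg | 10.5 | Mild | Meets the definition of accelerated hypertension (systolic at least 180 and diastolic at least 100); the bullet applies if other medication cannot control it, whatever the grade |
| Serum potassium abnormality | 10.7, 13.2 | Mild | No named criterion; being Mild, it falls outside the catch-all bullet at any value |

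The Table 8 column would not change if the values were more extreme, as long as function stayed unaffected. An investigator who does not use the table has no stated rule for any of the three.

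**Step 3: does another specified summary show the size of the abnormality?** Sections 12.7.2 and 12.7.4 specify listings, not tables. The AE tables of 12.7.1 are the only specified summary in which these events appear, and there they carry the investigator's grade.

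**Step 4: can 13.3 and 9.3.1 both be followed?** Yes. The hypertension, edema and diabetic criteria have their own thresholds, and heart failure is a named event. None of the four refers to Table 8. The tension lies in the fifth bullet. Its wording suggests that the events listed before it are themselves at least moderate, whereas Table 8 would grade some of them Mild. The bullet also depends on a grade that Table 8 cannot assign sensibly to a symptom-free finding.

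**Step 5: how large is the effect?** If all of about 60 enrolled subjects are dosed, each subject whose worst grade is affected moves the moderate-or-worse percentage by 1/60 = 1.7 points. For a subject to count, three things must hold: the site graded the event Mild, a magnitude-based scale would grade it moderate or worse, and the subject had no other moderate-or-worse AE. The documents give no information on how often these coincide.

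**The case against.** The best reply is that Table 8 does not bind anyone. Section 13.3 offers it as an aid, and the same section goes on to describe severity as the intensity of an event, with myocardial infarction as its example and no mention of function. An investigator may therefore grade an extreme laboratory value above Mild. This stands, and it rules out saying that such events will always be recorded as Mild. It does not remove the gap, because an investigator who sets the table aside is given no other criterion.

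Other safeguards exist. Laboratory and vital-sign changes are primary endpoints in their own right. Seriousness is classified separately and includes important medical events. AEs leading to discontinuation are tabulated. Section 12.4 speaks of a summary of the general safety profile that covers laboratory tests and vital signs, and section 12.1 defers the analysis to an SAP whose detailed text is not in the documents, so laboratory grading there cannot be excluded. These points limit the consequence. However, the sections that specify how laboratory and vital-sign data will be presented name listings only.

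A reader might infer that Table 8 contradicts 9.3.1. The documents do not support this: the named criteria operate regardless of grade, so the two sections can be followed together.

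A reader might also put a range on the bias, for example 3 to 18 of 60 subjects (5% to 30%). Those percentages only restate an assumed number of affected subjects; nothing in the documents supports them.

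Finally, rewriting the grade that sites record would not be neutral. More symptom-free abnormalities could then count as at least moderate under the last bullets of 9.3.1 and 9.3.2. This objection stands, and it is why the remedy should be confined to the analysis.

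**Conclusion.** The point holds in a limited form. The protocol has one AE severity scale. It is optional, it grades only by interference with usual function, and it gives no basis for grading a symptom-free laboratory or blood-pressure AE other than Mild. With listings as the only specified presentation of the underlying values, the severity summary for the first primary endpoint could understate harms such as hyperglycemia and hypertension.

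The direction follows from the wording where Table 8 is used: a symptom-free event cannot be graded above the lowest category. The size cannot be derived. It would need the rate of symptom-free laboratory and vital-sign AEs, how often sites use the table, and how often such subjects have no other moderate-or-worse AE. No decision rule is tied to severity, so the conclusion on tolerability is not shown to be wrong; it would rest on a summary that may be insensitive to known risks.

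The relation to 9.3.1 and 9.3.2 is a tension in wording, not a contradiction. The conclusion rests on the current protocol text and on the SAP not already containing a magnitude-based grading. This is a cheap improvement, not a fatal flaw.

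**What to change.** In sections 12.7.1 and 12.7.2 and in the SAP, add a table of each subject's worst on-treatment grade for laboratory and vital-sign values. Derive it from data already collected, using one named published grading table based on magnitude and fixed before the analysis. Show it beside the investigator-reported severity, and state that it is for analysis only and does not feed into dosing or discontinuation.

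State a rule for glucose, because section 10.7 allows fasted or nonfasted samples at every visit.

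Separately, the sponsor should reconcile Table 8 with the moderate-intensity wording in 9.3.1 and 9.3.2, and say how severity is to be assigned to laboratory and vital-sign AEs. No change to any dosing or stopping rule is proposed here.

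The cost is a short paragraph and one programmed table, with no new assessments. There are three drawbacks. More events may appear as moderate or severe. Derived and site grades will sometimes differ and need a sentence of explanation. Nonfasting samples and blood-pressure readings add some noise, since section 10.5 requires repeat blood-pressure measurement only at screening and baseline.
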